An exploratory study of the effect of tranexamic acid treatment on the progression of COVID-19
in outpatients

Study Protocol and Statistical Analysis Plan

NCT04338074

Date 05/03/2021

[name], PhD Principal Investigator
University of Alabama at Birmingham
Birmingham, AL 35294

Protocol Summary - in nontechnical, lay language

a. Summarize the purpose and objectives of this protocol in one short paragraph. The current proposal seeks to determine the effect of a 5 day treatment with oral tranexamic acid (TXA) on the outcomes of outpatients who are newly identified (within 72 hours of test result and within 7 days of onset of symptoms) as test positive for the SARS-CoV-2 virus. Subjects receiving COVID-19 testing within the UAB system will be identified and contacted by telephone, informed of the study with its potential risks/benefits. If they agree to proceed, they will be consented, randomized to TXA or placebo treatment. Because of concerns related to hypercoagulability in COVID-19 patients and with TXA treatment, all subjects will also be treated with prophylactic anticoagulation using the anticoagulant, apixaban 5 mg p.o. BID

b. Describe how outcomes will be measured for this protocol. The primary outcome of this study is the need for admission to a hospital due to COVID-19. Secondary outcomes include symptom progression and any other available medical information such as visible bruising.

Background - in nontechnical, lay language

A recent report in Physiological Reviews (attached) proposed that the endogenous protease plasmin acts on SARS-CoV-2 by cleaving a newly inserted furin site in the S protein portion of the virus resulting in increased infectivity and virulence. Patients with hypertension, diabetes, coronary artery disease, cerebrovascular illness, COPD and kidney dysfunction commonly have elevated levels of plasmin/plasminogen and it was proposed that this may be the mechanism for poorer outcomes in patients with these co-morbidities. A logical treatment that might blunt this process would be the inhibition of the conversion of plasminogen to plasmin. Fortunately, there is an inexpensive, commonly used drug, tranexamic acid, TXA, which suppresses this conversion and could be re-purposed for the treatment of COVID-19.

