Describe your ability to obtain access to the proposed population that will allow recruitment of the necessary number of participants: A Co-PI of this project, [name], is a faculty of the Infectious Disease Division of the Department of Medicine. She currently is responsible for Employee Health testing and is a member of her divisional task force related to COVID-19 studies at UAB. Identification of patients would be a cooperative effort with the members of the Infectious Disease Division.

d. Describe the inclusion/exclusion criteria:

Inclusion: a recent positive test (within 96 hours of testing; within 7 days of onset of symptoms) for COVID-19; currently an outpatient with no expected immediate hospitalization; English speaking and with phone/internet capability adequate for daily communication. At present, only RNA detecting COVID-19 tests are considered valid and will be the only ones accepted.

Exclusion: an immediate need for hospitalization; history of seizures; history of significant renal disease; history of hypercoagulation-related disorders including pulmonary thromboembolisms, deep venous thromboses, vision/ocular changes; recent or ongoing anticoagulation treatments; cardiac or other vascular stents; active bleeding; history of GI bleed; history of intracranial hemorrhage; pregnancy; use of estrogen-containing oral contraceptives; active malignancy

e. If participants will comprise more than one group or stratification, describe each group (e.g., treatment/intervention, placebo, controls, sham treatment) and provide the number of participants anticipated in each group. Subjects will be randomized into a TXA treatment group (n=50) and a Placebo group (n=50). There will be a post hoc analysis that uses stratification according to high vs. low risk for progression of COVID-19 based on age/comorbidities. Notably, 45% of adult Alabamians qualify for the high risk group: elderly, obesity, hypertension, diabetes, COPD, CAD.

f. Indicate which, if any, of the special populations listed below will be involved in the protocol. Include the Special Populations Review Form (SPRF) if indicated.

Employees or students at institution where research conducted

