2) Due to the possible risk of hypercoagulability being greater in the COVID-19 population, all subjects (both TXA and placebo groups) will also be asked to self-administer apixaban (5 mg p.o. BID), in an unblinded fashion as anticoagulation during the 5 day study period.

A minimal exposure “drive-by” interaction will occur in which there is a transfer of treatment materials (drugs and instructions) while the patient remains isolated in their vehicle. This is currently planned for a small component of the off-street parking area immediately adjacent to the 1917 Clinic located at [name]. This interaction will consist of conversation with either one of the investigators or one of the research nurses named in the IRB Personnel Form. As in all physical interactions with COVID-19 patients, study personnel would don appropriate personal protective equipment. Communication will either occur via cell phone or by talking loudly so it can be heard through the window. They will also have 24/7 access to research personnel by phone/internet to ask additional information.

Notably, this “drive-by” interaction has several advantages over the alternative (mailing medications/instructions to patients) in that it assures delivery and initiation of the treatments, it reduces the potential exposure of postal personnel to a known COVID-19 patient.

Contact after the “drive-by” interaction would be exclusively by telephone or via the internet.

All subjects will be contacted by telephone or internet daily and ongoing symptoms will be assessed for 7 days. In subjects with symptoms, additional contact(s) will be made at 3 day intervals for up to 30 days until resolution of any symptoms.

The primary endpoint for the study is hospital admission for COVID-19 within 7 days of enrollment.

b. What is the probable length of time required for the entire protocol (i.e., recruitment through data analysis to study closure)? 6 months

c. What is the total amount of time each participant will be involved? To primary endpoint – daily for 7 days after that, intermittently until resolution of symptoms – for up to a maximum of 30 days.

d. List the procedures, the length of time the procedure takes, the total # of times the procedure is performed, and indicate whether each is performed solely for research or would already be performed for treatment or diagnostic purposes (routine care) for the population.
-Insert additional table rows as needed.

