-If procedure is sometimes research and sometimes routine care, include on separate lines with number of times as each.

Procedure	Length of Time Required of Participants	Total # of Times the Procedure is Performed	Research (Res) –OR- Routine Care
Consent	1 hour	1	 Res  Routine
“Drive-by” interaction to pick up study drugs/placebo	30 min	1	 Res  Routine
Daily Phone or email Contact	20-30 min each contact	7 times until primary endpoint, then follow-up at 3 day intervals until symptoms resolve up to 30 days	 Res  Routine

f. Will participants be compensated? Yes No

If Yes, complete i-v.

- i. Type: (e.g., cash, check, gift card, merchandise): Gift card
- ii. Amount or Value: \$50
- iii. Method (e.g., mail, at visit): Received at time of “drive-by” interaction
- iv. Timing of Payments: (e.g., every visit, each month): once
- v. Maximum Amount of Compensation per Participant: \$50

Benefits

Describe the potential benefits of the research.

The participant may benefit directly from participation in this study. Clearly benefits to the patient and society if it is demonstrated that TXA reduces the severity of COVID-19. This pilot study is unlikely to demonstrate definitive results as it is not powered sufficiently for that endpoint (would require 200 patients per group for 50% reduction). It will, however, provide the necessary preliminary data needed for a larger multicenter trial of the same intervention. Its primary purpose is an assessment of safety and the generation of efficacy estimates for TXA.

Risks - in nontechnical, lay language

- a. List the known risks for participants as a result of participation in the research. This should not include the minimal risk of loss of confidentiality. However, it should include any physical, psychological, social,

economic, and/or legal risks. If there is a greater than minimal risk of loss of confidentiality describe why this is so. Do not list risks associated with the standard-of-care procedures.

NOTE: Risks included here should be included in the consent form or information sheet, as applicable.

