Patients interested in participating will be emailed a copy of the consent form. The PI/study personnel will verbally present the study by going over the consent form. The PI/study personnel will arrange a video (Zoom) conference with the subject and a witness (who may be someone already in the subject's household). The call will include the following: (1) Identification of who is on the call, (2) Review of the consent form by the PI/study personnel and answering any questions the subject may have, (3) Confirmation by the witness that the subject's questions have been answered, (4) Confirmation by the PI/study personnel that the subject is willing to participate in the study and sign the consent form while the witness is listening on the phone, (5) Verbal confirmation by the subject that they would like to participate in the study and that they have signed and dated the consent form.

The signed consent form then be scanned/photographed and emailed back to the PI/study personnel. A copy of the consent form signed by the investigator and witness will be placed in the study record. Following FDA guidelines, a hard copy of the consent form signed by the subject will not be retained (e.g., due to potential contamination of the document by infectious material).

Statistical Plan

Update (5/2/2021) The statistical plan for this study was to compare categorical data for the primary endpoint which was hospital admission during the 7 day treatment period. A simple Chi Square comparison was planned. Any secondary data were to be described qualitatively and not analyzed statistically.

In this truncated study, no subjects met the primary endpoint and there were insufficient data to perform any meaningful analysis.

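### Safety is one of two stated primary purposes, yet no harm beyond bruising, given as an example, is named as an outcome, and no safety rate, interval or by-arm comparison is planned

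*Combined protocol and SAP*

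**What the plan says.** The Benefits section concedes that the pilot is not powered for efficacy and then gives its purpose: "Its primary purpose is an assessment of safety and the generation of efficacy estimates for TXA". Safety is thus one of two joint purposes.

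The outcomes are set elsewhere. Protocol Summary, item b: "The primary outcome of this study is the need for admission to a hospital due to COVID-19", and then "Secondary outcomes include symptom progression and any other available medical information such as visible bruising". Protocol Procedures, item a, fixes the window: "The primary endpoint for the study is hospital admission for COVID-19 within 7 days of enrollment".

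The Statistical Plan, an update dated 5/2/2021, gives one analysis for the primary endpoint: "A simple Chi Square comparison was planned". For the rest: "Any secondary data were to be described qualitatively and not analyzed statistically".

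The Risks section (items a and b) discusses clotting, seizures, bleeding and visual disturbance. It says that participants are asked about signs of deep venous thrombosis and pulmonary embolism at the telephone contacts. On background treatment, Protocol Procedures, item a, states that "all subjects (both TXA and placebo groups) will also be asked to self-administer apixaban (5 mg p.o. BID), in an unblinded fashion".

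**The concern.** A stated purpose needs an outcome and a summary measure to carry it out. The efficacy purpose has both: admission within 7 days, compared between arms. The safety purpose has neither. The harms that worried the investigators enough to add an anticoagulant for everyone are not turned into counted events, and the only rule for non-primary data is qualitative description.

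At stake is what the pilot passes on. The Benefits section says its data are to support a larger multicenter trial of the same intervention. A sentence saying that no clots were seen, without a denominator or an interval, sounds reassuring even when the data exclude very little.

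**Working it through.** **1. From harm to outcome.** For each harm under Risks, the documents provide the following:

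- Thromboembolism: signs are asked about at the telephone contacts and used to direct the participant's care. It is not an outcome.
- Bleeding: visible bruising is an example within secondary information, with no definition, grade or window. No specific question is described.
- Seizure or altered mental status: depends on family members calling or seeking care. No specific question is described, and it is not an outcome.
- Visual disturbance: listed from post-marketing reports. No specific question is described, and it is not an outcome.
- Adverse events generally: ongoing symptoms are assessed daily for 7 days, but no adverse-event outcome is defined.

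No count by arm is planned for any of these.

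**2. The plan's own figure.** There is no safety figure to reproduce. The only sample-size figure is 200 per group for a 50% reduction (Benefits), which concerns admission. The documents give no control rate, alpha or power for it. Assuming 20% versus 10%, two-sided 0.05 and 80% power:

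n = [1.960·√(2·0.15·0.85) + 0.842·√(0.20·0.80 + 0.10·0.90)]² / 0.10² = (0.990 + 0.421)² / 0.01 ≈ 199.

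The figure is plausible, and this point does not depend on it.

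**3. What by-arm counts would show.** The input is 50 per arm (Participants, item e). Clopper-Pearson two-sided 95% limits for x events in n are: lower = Beta⁻¹(0.025; x, n−x+1), or 0 when x = 0; upper = Beta⁻¹(0.975; x+1, n−x). With x = 0 the upper limit is 1 − 0.025^(1/n).

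| Events | Exact 95% interval |
|---|---|
| 0/50 | 0 to 1 − 0.025^(1/50) = 7.1% |
| 1/50 | 0.05% to 10.6% |
| 2/50 | 0.5% to 13.7% |
| 0/100 (pooled) | 0 to 1 − 0.025^(1/100) = 3.6% |

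For the difference between arms (Newcombe), 0 versus 0 gives −7.1 to +7.1 percentage points, and 2 versus 0 gives −3.7 to +13.5.

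**4. How little a zero means.** If the true rate in an arm were 1.5%, the chance of seeing no event in 50 would be 0.985^50 = 47%. At 5% it would be 0.95^50 = 8%.

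**5. Truncated size.** The number enrolled is not given. Assuming 10 or 20 in an arm, zero events leaves upper limits of 1 − 0.025^(1/10) = 31% and 1 − 0.025^(1/20) = 17%.

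**6. Why no test.** With 50 per arm, Fisher's exact test gives p = 0.056 for 5 versus 0 and p = 0.027 for 6 versus 0. Only a gross excess would reach 0.05, so intervals are the informative summary.

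**The case against.** The best defence is that safety is being watched. Clot symptoms are asked about, bruising is named, and contact is daily for 7 days. Qualitative description may have been meant only to rule out testing and does not clearly forbid counting. The sentence also sits in a past-tense update to a truncated study.

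Much of this stands, and it limits what can be claimed:

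- A reader might infer that the trial collects no safety information, or cannot assess safety at all. The telephone questions and the bruising example contradict that. What is missing is definition, complete questioning and tabulation.
- A reader might take the Benefits sentence as promising the safety of TXA alone. The words naming TXA may attach only to the efficacy estimates, and the document says openly that both arms take apixaban. The results need only say what was compared.
- A reader might set 7.1% against the 1.4% seizure rate and the roughly 1.5% haemorrhagic rate under Risks. The first comes from high-dose intravenous use in cardiac surgery and the second from apixaban taken for more than 6 months. The document itself expects less risk here. Neither is an expected rate for this trial, and no rate is given for thrombosis.

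The core remains. Even if counting is permitted, nothing requires counts, denominators or intervals by arm, and no other safety analysis appears. That the update was written after truncation does not help, because it reports what the plan was.

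**Conclusion.** The point holds as a mismatch between a stated purpose and the analysis. Safety is one of two primary purposes, but the plan as written gives no safety event rate, interval or by-arm comparison. It should be corrected. It does not affect the admission endpoint.

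At the planned size, even a properly tabulated result would be coarse: with no events, rates up to 7.1% per arm, or 3.6% pooled, would remain compatible with the data. These limits assume 50 participants per arm, all with known status through day 7. After day 7 only participants with symptoms are contacted (Protocol Procedures, item a), so complete counts cannot be claimed beyond that day. The limits at 10 or 20 per arm are illustrations, because the documents do not give the truncated size.

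**What to change.** - Name the harms already listed under Risks as safety outcomes, with a short definition of each: thromboembolic event, bleeding, seizure or altered mental status, visual disturbance, and other adverse events.
- Ask about each of them at the existing daily contacts. For participants already followed, tabulate what was asked and say what was not.
- For these outcomes, replace the qualitative-only rule with the number of participants with each event, by arm and in total, through day 7. Give an exact 95% interval for each, zeros included, and no hypothesis test.
- Report events after day 7 separately, as incompletely ascertained.
- State in the results that the comparison is TXA plus apixaban versus placebo plus apixaban.

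The cost is a few added questions in the existing contact script, brief event definitions and one table. No extra participants or visits are needed. The drawback is a visibly imprecise safety statement, which is an accurate reflection of a pilot of this size.

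### The pilot is meant to generate efficacy estimates, but its only planned primary analysis is a chi-square test with no effect measure or confidence interval

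*Combined protocol and SAP*

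**What the plan says.** The Benefits section sets out what the pilot is for. It warns that "This pilot study is unlikely to demonstrate definitive results as it is not powered sufficiently for that endpoint", adding that a definitive study "would require 200 patients per group for 50% reduction". It then says the pilot will "provide the necessary preliminary data needed for a larger multicenter trial of the same intervention", and closes: "Its primary purpose is an assessment of safety and the generation of efficacy estimates for TXA".

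Item e of Participants (Screening and Selection) gives 50 subjects per arm. Item a of Protocol Procedures, Methods, and Duration makes the primary endpoint binary: admission for COVID-19 within 7 days of enrolment.

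The Statistical Plan is the only statistical section. On the primary endpoint it says "A simple Chi Square comparison was planned", and on everything else "Any secondary data were to be described qualitatively and not analyzed statistically". It ends with the outcome: "In this truncated study, no subjects met the primary endpoint and there were insufficient data to perform any meaningful analysis".

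**The concern.** A chi-square test answers whether the two admission rates differ by more than chance would explain. It does not say by how much, in which direction, or with what precision. A team sizing a larger trial needs a control-arm admission rate and a plausible range for the treatment effect, and a p-value supplies neither. The pilot is admittedly too small for the test to be decisive, so the most likely product of the plan is a non-significant p-value that tells the next team little. The admission counts do contain the wanted estimate. The plan does not say that it will be produced, on what scale, or with what interval.

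**Working it through.** **Search for an estimate elsewhere in the plan.** The secondary data are to be described in words only. The post hoc split by high and low risk (Participants, item e) names no effect measure. No risk difference, risk ratio, odds ratio, arm-level rate with precision, or confidence interval is specified anywhere.

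**The plan's own figure: 200 per group for a halving.** The documents give no control rate, significance level, sidedness or power, so these are assumptions. The usual formula is

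n = [1.960·√(2p̄(1−p̄)) + z_power·√(p_C(1−p_C) + p_T(1−p_T))]² / (p_C − p_T)²

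- 20% vs 10%, two-sided 5%, 80% power: (1.960·√0.255 + 0.842·√0.25)² / 0.01 = (0.990 + 0.421)² / 0.01 = 199.
- 25% vs 12.5%, two-sided 5%, 90% power: (1.082 + 0.698)² / 0.015625 = 203.
- Solving for exactly 200 gives control rates of 19.9% (80% power) and 25.3% (90% power).
- Allowing one- or two-sided 5% tests, 80% or 90% power, and a continuity correction or none, control rates from about 16% to 28% come within 3% of 200.

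**Power of the planned test.** I summed binomial probabilities over all possible tables in which the uncorrected Pearson statistic exceeds 3.841, for a true halving.

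| Control rate (assumed) | 50 per arm | 200 per arm |
|---|---|---|
| 20% | 30.3% | 81.1% |
| 25% | 37.1% | 90.2% |

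The same calculation at 50 per arm gives about 24% at a 16% control rate and 41% at 28%. Throughout the range, a non-significant result is the more likely one.

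**One illustrative table: 5/50 on TXA, 10/50 on placebo.**

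- Chi-square: 100·(5·40 − 10·45)² / (50·50·15·85) = 1.961, p = 0.161. Swapping the arms leaves it unchanged.
- Arm rates, exact (Clopper-Pearson) 95% CI: TXA 10% (3.3% to 21.8%); placebo 20% (10.0% to 33.7%).
- Risk difference: −10 points. The Wilson limits are 4.35% to 21.36% (TXA) and 11.24% to 33.04% (placebo). The Newcombe limits are therefore −0.10 − √(0.0565² + 0.1304²) = −24.2 points and −0.10 + √(0.1136² + 0.0876²) = +4.3 points. The Miettinen-Nurminen score interval is close, −24.7 to +4.3.
- Risk ratio: 0.50. The standard error of its log is √(1/5 − 1/50 + 1/10 − 1/50) = 0.510, so the 95% CI is 0.18 to 1.36.

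**What a successor trial gains.** With the placebo limits from this table in the formula above (halving, 80% power, two-sided 5%), the requirement runs from 434 per group at 10.0% to 104 at 33.7%, with 199 at 20%.

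**Average precision at 50 per arm.** The expected width of the Newcombe interval is 28.3 points for 20% vs 10% (coverage 95.7%) and 30.2 points for 25% vs 12.5% (coverage 95.1%).

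**The case against.** The strongest reply is that the Statistical Plan is a short, past-tense update written after the study was cut short, so its silence on estimates need not be a decision to omit them. A chi-square is computed from a 2×2 table. Anyone who sees that table can read off each arm's rate and the direction, and can work out a difference or ratio. That is fair: no data are missing, and the argument about direction bites only if the counts are withheld. But this is the only plan the documents contain, and it leaves the scale, the interval method and the reporting of precision to be chosen after the data are seen.

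A second reply is that low power is already disclosed. It is, and the power figures here reveal no new flaw. They show why estimation, rather than testing, has to carry the result.

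Third, the practical effect is now small. No admissions occurred, the number enrolled is not given, and a named effect measure can no longer be pre-specified. This largely stands. With no events the chi-square and the risk ratio are undefined, while the risk difference still has an interval: about ±7 points if 50 per arm had enrolled, but about ±28 points at 10 per arm. Nor should the original plan be blamed for this. At 20% and 10% with full enrolment, the chance of no admissions at all is (0.8 × 0.9)^50, about 7 in 100 million. That figure says nothing about the truncated study; at 10 per arm the chance is 0.72^10, about 4%.

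**Conclusion.** The concern holds. The stated purpose includes efficacy estimates, and the stated analysis specifies none. This follows from the text alone and does not depend on any assumed rate or on how the 200 per group was derived; nothing here shows that figure to be wrong.

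The size does rest on assumptions. With a control rate of 20% to 25% and a true halving, the planned test would miss significance about 63% to 70% of the time. The same counts would give a risk-difference interval averaging 28 to 30 points wide. That is imprecise, but it states the pilot's information openly. The 5 vs 10 table and the 104 to 434 range are illustrations from one hypothetical result. The point should be acted on because it touches a stated primary purpose and is cheap to repair. It does not invalidate the trial, and its main value now is for any larger trial that builds on this plan.

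**What to change.** State in the plan that the main output for the primary endpoint, reported beside the chi-square, is each arm's 7-day admission rate with an exact 95% CI and the risk difference (TXA minus placebo) with a Newcombe or score 95% CI. Add the risk ratio with its 95% CI when both arms have events, since a later trial may be sized on a relative reduction.

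For the ended study, if this is not already reported elsewhere, add one line labelled post hoc: 0/n in each arm with the exact upper limit, and the risk-difference interval. Say plainly that it may be nearly uninformative at small n.

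The cost is one sentence in the plan and a few minutes' computation from the same 2×2 table. No new data are needed and the chi-square stays.
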